5.2. Treatment Groups

This is a multicenter, open-label, increasing dose strength study of INCB050465 administered as 1 tablet QD. There are 2 cohorts and approximately 10 participants will be enrolled in Cohort 1, and approximately 15 participants in Cohort 2.

Cohort 1: INCB050465 1 mg QD for up to 12 weeks. At Week 6, participants who fulfill dose increase criteria (see definition below) will be offered INCB050465 2.5 mg QD for up to 6 weeks. If there are any tolerability issues in individual participants who received 2.5 mg, the dose may be decreased to 1 mg.

Cohort 2: INCB050465 2.5 mg QD for up to 12 weeks. If there are any tolerability issues in individual participants, the dose may be decreased to 1 mg.

Criteria for dose increase: (1) Continue to require transfusions by Week 6 visit, or (2) do not attain a meaningful clinical response (at least a stabilization ≥ 2 g/dL increase in hemoglobin from baseline to Week 6). Dose increases require sponsor preapproval (refer to Protocol, Section 6.6).

Participants will be summarized overall and based on the dose regimen initially assigned in the study.

5.3. Analysis Populations

5.3.1. Full Analysis Set

The FAS includes all participants enrolled in the study who receive at least 1 dose of INCB050465.

The FAS will be used for the summary of demographics, baseline characteristics, participant disposition, and analyses of all efficacy and safety data.

5.3.2. Treatment Extension Evaluable Population

Participants who apply at least 1 dose of INCB050465 in the extension period will constitute the TE evaluable population.

5.3.3. Pharmacokinetic/Pharmacodynamic Evaluable Population

The PK/PD population will include all participants who received at least 1 dose of study drug and provided at least 1 postdose blood sample (1 PK/PD measurement). The study pharmacokineticist will review data listings of participant dosing and sample records to identify participants to be excluded from the analysis.

6. BASELINE, EXPOSURE, AND DISPOSITION VARIABLES AND ANALYSES

[Appendix A](#) provides a list of data displays and sample data displays.

6.1. Baseline and Demographics, Physical Characteristics, and Disease History

6.1.1. Demographics

The following demographics will be summarized for the FAS: age, sex, race, ethnicity, weight, height, and BMI.

6.1.2. Baseline Disease Characteristics

The following baseline disease characteristics will be summarized for the FAS:

- Years since first onset of AIHA (< 2 years, 2-5 years, > 5 years)
- Type of AIHA (warm/cold/mixed type/other)
- Number of hospitalizations due to hemolytic anemia in the past year
- Failed therapies (no/yes [prednisone/rituximab/other])
- Transfusions in the past year (no/yes)
- Splenectomy received (no/yes)

6.1.3. Prior Therapy

Prior medication information for AIHA will be used to identify medication received by participants before enrollment into the study. Prior medications for AIHA will be summarized.

6.1.4. General Medical History

For participants in the FAS, general medical history will be summarized by assigned cohort. This summation will include the number and percentage of participants with significant medical history for each body system/organ class as documented on the eCRF.

6.2. Disposition of Participants

The number and percentage of participants who were treated, completed the study, discontinued study treatment with a primary reason for discontinuation, and discontinued from the study with a primary reason for withdrawal will be summarized for the treatment period (FAS) and the extension period (TE) separately. The number of participants enrolled by site will also be provided.

6.3. Protocol Deviations

Protocol deviations recorded on the eCRF will be presented in the participant data listings. A summary table of major Protocol deviations will also be provided for the treatment period (FAS) and extension period (TE) separately.

6.4. Exposure

For participants in the FAS and TE, descriptive statistics will be provided for duration of treatment, average daily dose, and total dose separately. Duration of treatment with INCB050465 is defined as the number of days from Day 1 to the date of last record of INCB050465 administration. In addition, daily usage of prednisone (or equivalent) will be summarized using descriptive statistics.

6.5. Study Drug Compliance

For participants in the FAS, overall compliance (%) for INCB050465 will be calculated for all participants as:

$$\text{Compliance (\%)} = 100 \times [\text{total dose taken}] / [\text{total intended dose}].$$

The total intended dose will be based on the earliest study day of permanent discontinuation of the study medication. Intended dose is defined as the sum of the doses prescribed by the investigator accounting both for planned dose reductions as well as those reductions or increases mandated by the investigator.

6.6. Prior and Concomitant Medication

For participants in the FAS, prior medications and concomitant medications will be coded using the WHO Drug Dictionary and summarized by WHO drug class and WHO drug term. Results will be summarized as number and percentage of participants with prior and concomitant medications by WHO drug term and WHO drug class.

7. EFFICACY

Sample data displays are provided in [Appendix A](#). All efficacy analyses are exploratory. Hence, no p-values will be provided and no multiple adjustment will be made.

7.1. Efficacy Hypotheses

Not applicable.

7.2. Efficacy Parameters

A CR for a given visit is attained if the following 2 conditions are satisfied:

1. Hemoglobin ≥ 12 g/dL.
2. Last transfusion occurred > 1 week before the date of visit.

A PR for a given visit is achieved if the following 2 conditions are satisfied:

1. Hemoglobin 10-12 g/dL or ≥ 2 g/dL increase from baseline.
2. Last transfusion occurred > 1 week before the date of visit.

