6.7.1.2. Folic Acid, Vitamin B12, or Iron Deficiencies

Participants who are noted to be deficient in folic acid, vitamin B12, or iron should have replacement determined by the investigator as per current standard of care.

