8.1.5. Prior and Concomitant Medications and Procedures

Prior and concomitant medications and procedures will be reviewed to determine participant eligibility. All concomitant medications and measures must be recorded in the eCRF, and any medication received or procedure performed within screening period before enrollment and up to the end of the follow-up period (see Table 1) will be recorded in the eCRF. The medication record will be maintained after signing the ICF to document concomitant medications, including any changes to the dose or regimen. Concomitant medications include any prescription, overthe-counter, or natural/herbal preparations taken or administered during the study period. Concomitant treatments and/or procedures that are required to manage a participant's medical condition during the study will also be recorded in the eCRF.

Extension Period

Use of concomitant medications should be monitored as described in Table 2 for participants in the extension period of the study to verify that participants are not taking any concomitant medication prohibited per Section 6.7.3.

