8.3.5.2. Vitamin B12 and Folic Acid

Vitamin B12 and folic acid will be tested at screening. Participants who are deficient in either folic acid or vitamin B12 will have replacement determined by the investigator as per standard of care.

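### SAP 7.2 screens response only for transfusion, so a hemoglobin rise after newly started iron, B12 or folate replacement can count as response to INCB050465

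*SAP*

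**What the plan says.** **Response rule.** SAP 7.2 gives each response two conditions. For CR the first is "Hemoglobin ≥ 12 g/dL"; for PR it is "Hemoglobin 10-12 g/dL or ≥ 2 g/dL increase from baseline". The second is the same for both: "Last transfusion occurred > 1 week before the date of visit". SAP 7.3 counts a participant who meets the rule at a single visit in the Week 6 to 12 window. Baseline is the last pre-dose value (SAP 4.1.3).

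**What the Protocol had in addition.** Protocol Sections 1 and 3 also required the hemolytic markers to normalize for CR and PR. SAP 10.1 records that this part was dropped from the primary endpoints. Marker normalization remains as a separate secondary endpoint (SAP 7.4, Table 2.2.6).

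**Replacement.** Protocol 8.3.5.2 states "Vitamin B12 and folic acid will be tested at screening", and 8.3.5.3 adds iron studies for everyone at screening. Under 6.7.1.2, "Participants who are noted to be deficient in folic acid, vitamin B12, or iron should have replacement determined by the investigator"; 8.3.5.2 repeats this for the two vitamins. Neither section gives a start date. The criteria in Protocol 5.1 and 5.2 do not name deficiency, and they do not ask for correction or a stable supplement dose before Day 1. Screening lasts at most 28 days.

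**Records.** Protocol 8.1.5: "All concomitant medications and measures must be recorded in the eCRF". The SAP summarizes and lists these medications (6.6, Table 1.4.3, Listing 1.4.1) but does not relate them to response.

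**The concern.** The transfusion condition shows that the plan does not want a hemoglobin rise from another cause to count as response. The rule stops at transfusion, although the Protocol itself provides for a second treatment that can raise hemoglobin. Without the marker condition, nothing in the SAP's definition of response asks whether hemolysis has lessened. Without a control arm, no comparison absorbs a replacement effect.

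At stake is how the CR and PR proportions are read. The study is exploratory, but SAP 10.1 says the Week 12 analysis is meant to support publications and a possible Phase 3 plan in CAD. In cohorts of 10 and 15, one or two participants change the picture.

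**Working it through.** **1. The plan's own figures.** The documents give no figure on this point. Their only stated probabilities concern detecting at least one adverse event at a 20% rate (Protocol 10.1, SAP 3.3). Both reproduce: 1 − 0.8^10 = 0.893 (stated as above 89%) and 1 − 0.8^15 = 0.965 (stated as above 96%). They do not bear on response attribution.

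**2. How small a rise can count.** Entry hemoglobin is 7 to 10 g/dL (Protocol 5.1, criterion 4). PR needs either 10 g/dL or a gain of 2 g/dL, so the smallest qualifying rise from baseline b is min(2, 10 − b). CR needs 12 − b.

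| Baseline (g/dL) | Smallest rise for PR | Rise for CR |
|---|---|---|
| 7.0 | 2.0 | 5.0 |
| 8.0 | 2.0 | 4.0 |
| 8.5 | 1.5 | 3.5 |
| 9.0 | 1.0 | 3.0 |
| 9.5 | 0.5 | 2.5 |
| 10.0 | 0 | 2.0 |

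For a participant who enters near the top of the range, a modest contribution from replacement is enough for PR. It matters less for CR.

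**3. Weight of one participant.** 1/10 = 10.0 points in Cohort 1, 1/15 = 6.7 points in Cohort 2, 1/25 = 4.0 points overall.

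**4. Illustration under assumed rates.** Let d be the share of participants who are deficient and newly replaced, and q the chance that replacement alone brings one of them to PR level. Neither is in the documents. With true drug response p, and taking the two effects as independent, the apparent rate is p + (1 − p)·d·q. With no drug effect, the chance of at least one false responder among n is 1 − (1 − d·q)^n.

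| Assumed d, q | Apparent rate, p = 0 | Apparent rate, p = 20% | At least one false responder, p = 0: n = 10 / 15 / 25 |
|---|---|---|---|
| 5%, 25% | 1.3% | 21% | 12% / 17% / 27% |
| 10%, 50% | 5% | 24% | 40% / 54% / 72% |
| 30%, 75% | 22.5% | 38% | 92% / 98% / above 99% |

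The width of this range shows that the documents do not determine the size. If nobody newly started replacement, d = 0 and the effect is nil.

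**5. Do other provisions close the gap?** Marker normalization (Table 2.2.6) is tabulated by visit for the group, not for responders. Listing 1.4.1 (medications) and Listing 2.1 (hemoglobin) are by participant, so a reader could match them by hand, but no output does so. Exclusion 15 lets the investigator exclude a condition that would cloud interpretation of the data. It does not name deficiency, and 6.7.1.2 allows for deficient participants within the study.

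**The case against.** The strongest reply is that the chain has several uncertain links. A deficient participant must enroll, must newly start replacement, and must cross a threshold because of it. Entry requires hemolytic anemia with serological evidence, so deficiency would add to the anemia rather than explain it. Replacement begun early in screening may already be partly reflected in baseline. Some participants may have been on supplements earlier; the Amendment 1 rationale in Protocol Appendix D mentions folic acid use. All of this stands, and it is why no size can be given.

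It can also be said that planned outputs help. Marker changes are secondary and PD endpoints, and with about 25 participants a manual cross-check is feasible. That also stands, but as a partial check left to the reader.

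Two further points have weight. Replacement is one of several influences outside the rule: Protocol 6.7.2 allows corticosteroids through end of treatment, and the rule does not filter those either. And discounting every visit after replacement starts can discard true drug responses. The first does not remove the gap. The second governs how the supportive result must be labelled.

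A reader might infer that replacement necessarily starts close to Day 1 and acts through Weeks 6 to 12. The documents do not support this, because Protocol 6.7.1.2 and 8.3.5.2 give no start date. A reader might also put a number on those exposed, for example 10% to 20% of 25, which is 2.5 to 5 participants. Nothing in the documents supports such a rate, and being exposed is not the same as being misclassified.

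**Conclusion.** The gap is real on the text. SAP 7.2 excludes transfusion effect and nothing else, the marker condition is gone from the primary endpoints, and the Protocol provides for replacement without requiring correction or a stable dose before Day 1. A rise caused by newly started replacement can therefore count as response, with as little as 0.5 g/dL sufficing for PR from a baseline of 9.5 g/dL.

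The size is unknown and could be zero. What can be said is the weight of each misattributed responder: 10 points in Cohort 1, 6.7 in Cohort 2, 4 overall. The rates in the illustration rest on assumed d and q.

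It would go too far to conclude that the response proportion is biased upward. It can be, if the conditions above are met in at least one participant. Nor does the point show that the futility rule in Protocol 4.1 and 9.6 is weakened: that rule sits in the Protocol, whose response definition still includes marker normalization. The point justifies a supportive analysis and a flag, not a change to the primary endpoint.

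**What to change.** In SAP 7.3, keep the primary definition and add a supportive CR/PR summary beside the main result:

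- Visits after a new start or an increase of iron, B12 or folate replacement, for a deficiency recorded at or after screening, do not count as response.
- Stable supplementation from before screening is exempt.
- State which record establishes the deficiency (laboratory result or recorded indication), since the documents set no cutoff.
- Label the result a conservative lower bound, not a corrected rate.
- Flag these participants in Listing 2.1 and show their hemolytic-marker status at the response visit, so that a rise with normalized markers can be told from one without.
- If no participant newly started or increased replacement, state that in one sentence; the summary is then unnecessary.

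The cost is a short SAP addition and some programming; screening results and concomitant medications are already collected. The downside is that true drug responses can be discarded: a participant who started replacement during screening can never be a responder in this summary. Clinical management does not change.

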6.6. Dose Modifications

6.6.1. Criteria and Procedures for Dose Increases of Study Drug

At Week 6, participants may be eligible for a dose increase. Due to the need to receive clinical laboratory results and to consult with the sponsor as needed prior to increasing the dose, investigators may implement the dose increase either at an unscheduled drug dispensing visit between the Week 6 and Week 8 visits or at the scheduled Week 8 visit. Any other requests for dose increase at alternate times may be considered on an individual basis in consultation with the sponsor. Individual participants in Cohort 1 may increase from INCB050465 1 mg QD to 2.5 mg QD with sponsor preapproval in the following circumstances, provided that protocol eligibility criteria are met at the time of escalation:

- Dose increase criteria, defined as the following:
 - The participant continues to require transfusions by the Week 6 visit or
 - The participant does not attain a meaningful clinical response (at least a stabilization ≥ 2 g/dL increase in hemoglobin from baseline to Week 6).
- The investigator determines there has not been a clinically meaningful response in hemoglobin and other hemolysis parameters.
- The participant is otherwise tolerating the current dose and has not had any drug-related adverse events.
- In the opinion of the investigator, the participant does not have a concurrent condition or circumstance that would complicate the dose escalation or PK sampling, or pose an increased risk.

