2.2. Objectives and Endpoints

Objectives	Endpoints
Primary	

• To evaluate the efficacy of INCB050465 in the treatment of participants with AIHA.	
• Proportion of participants attaining a CR (defined as hemoglobin ≥ 12 g/dL not attributed to transfusion effect*) at any visit from Week 6 to Week 12.• Proportion of participants attaining a PR (defined as hemoglobin 10-12 g/dL or at least ≥ 2 g/dL increase from baseline not attributed to transfusion effect) at any visit from Week 6 to Week 12. 
*No transfusion effect definition: > 1 week since last transfusion.

• To evaluate the safety of INCB050465 administered as repeat doses in participants with AIHA.	
• Safety and tolerability will be assessed by monitoring AEs, measuring vital signs and ECGs, and conducting clinical laboratory blood and urine sample assessments.
Secondary	

• To further evaluate the efficacy of INCB050465 in the treatment of participants with AIHA.	
• Proportion of participants attaining a CR during postbaseline visits.• Proportion of participants attaining a PR during postbaseline visits.• Proportion of participants attaining a ≥ 2 g/dL increase in hemoglobin from baseline.• Mean, change, and percentage change from baseline of hemoglobin.• Proportion of participants requiring transfusions.• Proportion of participants who achieve normalization of hemolytic markers. (Hemolysis markers: hemoglobin, haptoglobin, LDH, reticulocyte count, total bilirubin, and direct/indirect bilirubin.)• Change of daily usage of prednisone.• FACIT-F subscale assessment.

• To evaluate the PK effects of INCB050465.	
• PK endpoints: C_{\max}, t_{\max}, C_{\min}, AUC_{0-t}, and CL/F.

Objectives	Endpoints

• To evaluate the PD effects of INCB050465.	
• Change from baseline in PD markers: reticulocyte count, DAT for IgG and C3b, cold agglutinin levels, haptoglobin, total bilirubin, direct/indirect bilirubin, LDH, and complement assessment (CH50, C3, and C4).

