7.3. Analysis of Primary Efficacy Parameters

The primary endpoints include:

1. Proportion of participants attaining a CR at any visit from Week 6 to Week 12 and
2. Proportion of participants attaining a PR at any visit from Week 6 to Week 12

The primary endpoints will be summarized using descriptive statistics.

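### The CR/PR rule looks back only 7 days for transfusions, so a participant still being transfused at longer intervals can count as a responder, mainly as PR, and no planned table would show it

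*SAP*

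**What the plan says.** SAP 7.2 sets two conditions for each response at a visit. For CR they are "Hemoglobin ≥ 12 g/dL" and "Last transfusion occurred > 1 week before the date of visit". For PR they are "Hemoglobin 10-12 g/dL or ≥ 2 g/dL increase from baseline" and the same transfusion condition. The endpoint table in SAP 2.2 gives the same rule ("No transfusion effect definition: > 1 week since last transfusion"), as does Protocol section 3.

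The primary endpoint in SAP 7.3 is met by a single visit: "Proportion of participants attaining a CR at any visit from Week 6 to Week 12", and likewise for PR. No confirming visit is required. Protocol Table 1 places the visits at Weeks 6, 8, 10 and 12, each ± 3 days.

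The Protocol definition also required normalization of hemolytic markers. SAP 10.1 records that this part was removed, which leaves hemoglobin and the look-back.

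SAP 7.4 item 5 classes a participant as requiring transfusions at a visit only if the last one fell within 7 days of it. In Appendix A, Table 2.2.5 reports that endpoint, and Listings 2.1 and 2.2 list hemoglobin and transfusions. No table crosses response with recent transfusion.

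Protocol 6.6.1 gives, among the Cohort 1 dose-increase criteria, "The participant continues to require transfusions by the Week 6 visit", with no look-back stated.

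**The concern.** A transfusion 8 or more days before a visit is ignored when that visit is classified. What matters is the interval between transfusions compared with 7 days. Weekly transfusion is always caught, and anything less frequent can slip through at some visit. With the marker condition gone, nothing else in the SAP definition separates hemoglobin recovered on drug from hemoglobin still partly supported by transfused cells.

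The study has no control arm and tests no hypothesis, so the descriptive proportions are the efficacy result. SAP 10.1 says the Week 12 interim analysis supports publications and a possible Phase 3 plan in CAD. A reader of the planned tables could not tell how many responders were still being transfused: under item 5, a CR or PR visit is by construction a visit without a transfusion requirement.

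**Working it through.** **The plan's own figure.** The only computed figures are the chances of seeing at least one AE at a 20% rate: 1 − 0.8^10 = 89.3% and 1 − 0.8^15 = 96.5%. Both reproduce the stated > 89% and > 96%. They do not bear on this point.

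**Inputs from the documents.** Nominal visit days are 42, 56, 70 and 84 (Protocol Table 1). The transfusion condition is a gap of more than 7 days (SAP 7.2), and one passing visit suffices (SAP 7.3). Entry hemoglobin is 7 to 10 g/dL (Protocol 5.1).

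**Assumption.** The documents give no transfusion interval. I take a fixed interval T of 7, 10, 14, 21 or 28 days, with every starting phase equally likely.

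**Step 1: transfusion condition alone.** For phase p = 0, …, T − 1, the gap at a visit on day v is (v − p) mod T. A visit passes if the gap exceeds 7. A transfusion on the visit day can count as before the visit (gap 0) or after it (gap T), and the ranges below span the two conventions.

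| T (days) | Passes at Week 6 | Passes at one or more visits | Visits passed, min-max (same-day before / after) |
|---|---|---|---|
| 7 | 0% | 0% | 0-0 / 0-0 |
| 10 | 20-30% | 80-90% | 0-1 / 0-2 |
| 14 | 43-50% | 43-50% | 0-4 / 0-4 |
| 21 | 62-67% | 100% | 1-3 / 2-3 |
| 28 | 71-75% | 100% | 2-4 / 2-4 |

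Example for T = 14: 6 or 7 of 14 phases pass (6/14 = 43%, 7/14 = 50%). Visits are also 14 days apart, so those phases pass at all four visits. With visits varied at random within ± 3 days, and a same-day transfusion counted as before the visit, the shares at one or more visits are 0%, 60%, 72%, 100% and 100%.

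**Step 2: hemoglobin condition.** From baseline b within 7-10 g/dL, PR needs a rise of min(10 − b, 2) g/dL and CR needs 12 − b, which is at least 2 g/dL. Assume, from outside the documents, that a transfusion adds 1-2 g/dL and that 25-90% of this remains at days 8-13. The residual is then 1 × 0.25 = 0.25 to 2 × 0.90 = 1.8 g/dL.

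- PR from the residual alone needs b ≥ 10 − 1.8 = 8.2 g/dL at the top of the range and b ≥ 10 − 0.25 = 9.75 g/dL at the bottom.
- At b of 7-8 g/dL, PR needs 2 g/dL, above the assumed maximum.
- CR needs at least 2 g/dL, also above that maximum.

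**Step 3: weight of one participant.** 1/10 = 10 points in Cohort 1, 1/15 = 6.7 in Cohort 2, 1/25 = 4 overall. Among the approximately 5 CAD participants planned for Cohort 2, one is about 20 points.

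**Step 4: longer look-backs.** Share passing at one or more visits on nominal days:

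| Look-back | T = 7, 10, 14 | T = 21 | T = 28 |
|---|---|---|---|
| > 14 days | 0% | 86-100% | 93-100% |
| > 21 days | 0% | 0% | 43-50% |
| > 28 days | 0% | 0% | 0% |

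**The case against.** The one-week rule is explicit and identical in both documents, and all efficacy analyses are exploratory. The documents offer no basis for preferring 14, 21 or 28 days. That stands, and it is why the definition should stay and the longer windows should enter only as sensitivity analyses.

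Baseline may itself be transfusion-supported, since neither document requires a transfusion-free period before it. A participant on a steady schedule might then show little further rise. This also stands: it lowers the likely number affected, although someone with a baseline at or just under 10 g/dL needs almost no rise for PR.

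The listings permit a check by hand in about 25 people. True, but a reader of the summary tables would not see the result.

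Three stronger readings are tempting, and the documents do not support them:

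- **That Protocol 6.6.1 calls transfused participants non-responders, so the endpoint contradicts it.** It does not use that label. It is a dosing rule for Cohort 1, it offers transfusion need as an alternative to lack of response, and it has a separate bullet, "The investigator determines there has not been a clinically meaningful response in hemoglobin and other hemolysis parameters". What can be said is that its transfusion clause states no window while the SAP looks back 7 days.
- **That transfusion alone would produce CR.** Under the assumed residual it would not.
- **That the two-week visit spacing is the cause.** It affects how often a schedule passes, but the gap arises from transfusion intervals longer than 7 days.

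**Conclusion.** The point holds in a limited form and should be addressed. The transfusion condition does not screen out participants transfused less often than weekly: 43-100% of regular schedules at 10- to 28-day intervals pass at one or more visits on nominal days. These shares are ceilings on misclassification, not estimates of it. They rest on assumed fixed intervals and ignore the hemoglobin condition, and the number of participants affected cannot be derived from the documents.

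The risk falls mainly on PR at a baseline near 10 g/dL. For CR, transfusion could add to a partial drug effect but would not suffice alone under the assumed residual of at most 1.8 g/dL. No error rate or power statement changes. The consequence is a possible upward bias in uncontrolled response proportions, at 10, about 7 or 4 points per participant, that the planned tables would not show.

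**What to change.** 1. Leave the primary definition in SAP 7.2 as stated.
2. Add to SAP 7.3 and Appendix A a prespecified sensitivity version of Tables 2.1.1 and 2.1.2 in which CR or PR also requires no transfusion in the 14, 21 and 28 days before the response visit. All three are useful, because 14 days closes the gap only for transfusions every two weeks or more often.
3. Report by cohort how many CR and how many PR participants had any transfusion between Week 4 and the response visit.
4. State how a transfusion on the visit day is counted, since this moves the shares above.
5. Reconcile the transfusion clause of Protocol 6.6.1 with the look-back in SAP 7.2 and SAP 7.4 item 5, or state that the windows differ on purpose.

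The cost is SAP wording and one derivation from transfusion dates already planned for Listing 2.2. The downside is that the sensitivity rates can only be equal to or lower than the primary ones. If no responder was recently transfused, they will agree and the primary result will be easier to defend.

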9.6. Data Monitoring Committee

There will be no formal Data Monitoring Committee. However, a Safety Review Committee, which will include the sponsor's medical monitor, pharmacovigilance representative, and statistician, as well as the investigators, will conduct meetings via teleconference on a regular basis to review emerging safety and clinical response data and dose modifications. Recommendations from this committee may include the option to expand study of Cohort 1, pending review of the efficacy response and adverse event data.

If there is no clinical response (CR or PR) by Week 12 in the first cohort of 10 participants, including those who receive dose escalation to 2.5 mg, the study will be stopped for futility.

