2.1 Primary Efficacy		
2.1.1	Summary of Participants Attaining a Complete Response at any Visit From Week 6 to Week 12	FAS
2.1.2	Summary of Participants Attaining a Partial Response at any Visit From Week 6 to Week 12	FAS

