2.2 Secondary Efficacy		
2.2.1	Summary of Participants Attaining a Complete Response by Visit	FAS
2.2.2	Summary of Participants Attaining a Partial Response by Visit	FAS
2.2.3	Summary of Participants Attaining a ≥ 2 g/dL Increase in Hemoglobin From Baseline	FAS
2.2.4	Summary of Hemoglobin by Visit	FAS

Table No.	Title	Population
2.2.5	Summary of Participants Requiring Transfusions	FAS
2.2.6	Summary of Participants Achieving Normalization of Hemolytic Markers by Visit	FAS
2.2.7	Summary of Daily Usage of Prednisone by Visit	FAS
2.2.8	Summary of FACIT-F Subscale by Visit	FAS
Safety		

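### SAP 7.2 does not exclude complete responders from PR, so for baselines of 10 g/dL or less the primary PR proportion (Table 2.1.2) is really CR or PR

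*SAP*

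**What the plan says.** SAP 7.2 sets two conditions for each response at a visit. For CR the hemoglobin condition is "Hemoglobin ≥ 12 g/dL"; for PR it is "Hemoglobin 10-12 g/dL or ≥ 2 g/dL increase from baseline". The second condition is the same for both: the last transfusion was more than a week before the visit.

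SAP 7.3 turns these visit-level rules into two separate primary proportions. The second is "Proportion of participants attaining a PR at any visit from Week 6 to Week 12". Appendix A gives each its own table: 2.1.1, "Summary of Participants Attaining a Complete Response at any Visit From Week 6 to Week 12", and 2.1.2, "Summary of Participants Attaining a Partial Response at any Visit From Week 6 to Week 12". By-visit Table 2.2.2, "Summary of Participants Attaining a Partial Response by Visit", uses the same PR rule. SAP 5.2 sets the columns: "Participants will be summarized overall and based on the dose regimen initially assigned in the study".

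Protocol Section 3 has the same uncapped 2 g/dL limb for PR, with CR set above 12 g/dL and normalization of hemolytic markers required for both. SAP 10.1 records that the marker requirement was removed and the hemoglobin range changed. It does not mention overlap between CR and PR. Protocol 9.6 names the union separately in the futility rule: "If there is no clinical response (CR or PR) by Week 12 in the first cohort of 10 participants". No table title in Appendix A gives a combined or best response.

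**The concern.** A reader of two primary tables titled complete and partial response will take them as separate categories, and the Protocol's own phrase for the union supports that reading. The SAP rules do not deliver it, for two reasons.

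- **Visit level.** The 2 g/dL limb of PR has no upper hemoglobin limit and there is no clause excluding CR. Low-baseline participants who reach CR therefore also meet PR at that same visit.
- **Participant level.** Because attainment at any one visit counts, someone who passes through 10-12 g/dL and later reaches 12 or more enters both tables, even if each visit were classified exclusively.

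At stake is the interpretation of a primary efficacy figure. Read as labelled, the PR row overstates partial response, and adding the rows counts complete responders twice. SAP 10.1 says the Week 12 analysis is meant to support publications and a possible Phase 3 plan, so the figure is likely to be reused away from its definition.

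**Working it through.** The plan states no response rate, so there is no figure of its own to reproduce on this point. Its only numerical design figure, the chance of seeing at least one adverse event at a 20% rate, does reproduce (1 − 0.8^10 = 0.893; 1 − 0.8^15 = 0.965), but it has no bearing here.

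**Inputs**
- CR and PR rules and the shared transfusion condition: SAP 7.2.
- Eligible hemoglobin 7 to 10 g/dL: Protocol 5.1, criterion 4.
- Analysis baseline is the last nonmissing pre-dose value: SAP 4.1.3.
- Planned sizes of about 10, 15 and 25: SAP 3.3.

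**Step 1: algebra.** If baseline B ≤ 10 and hemoglobin H ≥ 12, then H − B ≥ 12 − 10 = 2. The hemoglobin condition for PR is met and the transfusion condition is common, so every CR visit is a PR visit.

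**Step 2: enumeration.** In 0.1 g/dL steps, B from 7.0 to 10.0 gives 31 values and H from 12.0 to 18.0 gives 61. Of the 31 × 61 = 1891 CR pairs, 1891 meet PR, and the count is unchanged if 12.0 is left out of the 10-12 limb. With the Protocol's cut above 12, 31 × 60 = 1860 pairs are CR and 1860 meet PR.

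**Step 3: baselines above 10.** The last pre-dose value can differ from the value that qualified the participant. Reading 10-12 as inclusive, H of exactly 12.0 meets both rules at any baseline. Other CR values can fail PR:

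| Baseline (g/dL) | CR values meeting PR (of 61) | CR values failing PR |
|---|---|---|
| 10.1 | 61 | none |
| 10.2 | 60 | 12.1 |
| 10.3 | 59 | 12.1-12.2 |
| 10.5 | 57 | 12.1-12.4 |
| 11.0 | 52 | 12.1-12.9 |

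With such participants present, the PR row is strictly neither partial response nor overall response.

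**Step 4: the any-visit overlap.** Take B = 8.5 and H = 11.0, 11.8, 12.4, 12.6 at Weeks 6, 8, 10 and 12, with no recent transfusion. The rises are 2.5, 3.3, 3.9 and 4.1.
- As written: PR at 4 of 4 visits and CR at 2 of 4, so counted in both primary tables.
- With a visit-level exclusion of CR: PR at Weeks 6 and 8, CR at Weeks 10 and 12, so still in both tables.
- With best response: CR only.

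**Step 5: size.** Compared with best-response PR, each complete responder with B ≤ 10 adds 1/10 = 10.0 percentage points in Cohort 1, 1/15 = 6.7 in Cohort 2 and 1/25 = 4.0 overall.

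The counts below are assumed for illustration, with all baselines ≤ 10:

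| N | CR | PR only | CR row | PR row as written | Best-response PR | Sum of rows as written | True CR or PR |
|---|---|---|---|---|---|---|---|
| 15 | 6 | 3 | 40% | 60% | 20% | 100% | 60% |
| 25 | 5 | 5 | 20% | 40% | 20% | 60% | 40% |
| 25 | 8 | 4 | 32% | 48% | 16% | 80% | 48% |
| 25 | 10 | 3 | 40% | 52% | 12% | 92% | 52% |

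Exact (Clopper-Pearson) 95% intervals for the first row: CR 6/15, 16-68%; best-response PR 3/15, 4-48%; CR or PR 9/15, 32-84%.

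**The case against.** The strongest reply is that the endpoints are worded as attainment at any visit, and nested attainment endpoints are coherent. A participant at 11 g/dL in Week 6 and above 12 in Week 10 did attain a PR at a visit. Nothing in the plan says the two proportions will be added. The analyses are exploratory without p-values (SAP 7), and within the eligibility range PR-only can be recovered as Table 2.1.2 minus Table 2.1.1. The table shells mentioned in Appendix A are not in the text reviewed and could hold a hierarchy or a footnote. The documents give no response rate, so the real inflation is unknown and would be zero with no complete responders.

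Much of this limits the weight of the point without removing it. A nested reading is possible, but then the title of Table 2.1.2 is wrong for what it counts, and the reader is not told to subtract. Subtraction can also fail once a baseline is 10.2 or higher. A rule in the shells cannot be excluded, but SAP 7.2 is the governing definition and contains none. SAP 8.3.1 adds a laboratory baseline rule that favors scheduled over unscheduled values. It can change which value is baseline, but not a result conditional on that value being 10 or less.

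One part stands in full: best response changes the primary endpoint as worded and should be recorded as such.

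**Conclusion.** The concern holds. For every participant with an analysis baseline of 10 g/dL or less, PR under SAP 7.2 contains CR, so the primary PR proportion equals the proportion with CR or PR. Each such complete responder raises the PR row by 10.0, 6.7 or 4.0 percentage points (Cohort 1, Cohort 2, overall) relative to best-response PR. The total inflation depends on the number of complete responders, which the documents do not predict.

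The containment rests only on the written rules and on the baseline condition. Baselines above 10 should be few, since eligibility is reviewed at screening and Day 1, but that is an inference. The overlap was inherited from the Protocol; SAP Amendment 1 left it in place and added a tie at exactly 12 g/dL. Nothing is tested, the CR row is correct, and the futility rule already uses the union. This should be fixed because a primary figure carries the wrong label.

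**What to change.** In SAP 7.2 and 7.3, assign each participant one best response over Weeks 6 to 12:

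- CR if any visit meets CR;
- PR if no visit meets CR and at least one meets PR;
- otherwise non-responder.

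Report CR, PR (best response) and CR or PR in one table, by initial cohort and overall, with exact 95% confidence intervals. In by-visit Tables 2.2.1 and 2.2.2, count a visit as PR only if it does not meet CR. That visit-level clause is not enough for the primary table, as Step 4 of the working shows. An optional row, not needed to remove the overlap, could show best-response PR participants who qualify by the 10-12 g/dL limb only: those with no Week 6-12 visit that has both a rise of at least 2 g/dL and the transfusion condition met.

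If the sponsor prefers to keep the any-visit wording, the minimum is to state that PR includes CR and to add a row computed as the union. That avoids double counting but still gives no partial-response figure.

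The cost is SAP wording, an entry in SAP 10.1 for the change to the primary endpoint, and a few table rows. No new data are needed, since hemoglobin and transfusions are already planned as Listings 2.1 and 2.2. The PR figure becomes smaller; the CR thresholds, the CR figure and the futility rule do not change.
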